10.2 Recording adverse events

Reported symptoms and illnesses will be reviewed by the study doctor and discussed with the PI as to causality and expectedness of the event, and a decision made as to whether this qualifies as an SAE or SUSAR. Reporting of SAEs and SUSARs will follow established sponsor SOPs and to the competent authority and research ethics committee (REC), if applicable. An independent data monitoring committee will assess safety data during the course of the trial.

All adverse events will be recorded in the paper CRF (which is the source data), whether believed to be related or unrelated to the treatment.

All SERIOUS adverse events must be recorded in the CRF and AE log.

If the investigator suspects that the disease has progressed faster due to the administration of the IMP, then she/he will report this as an unexpected adverse event to the sponsor.

Clinically significant abnormalities in the results of objective tests (e.g. ECG) may also be recorded as adverse events. If the results are not expected as part of disease or IMP, these will also be recorded as unexpected.

All adverse events will be recorded with clinical symptoms and accompanied with a simple, brief description of the event, including dates as appropriate.

All adverse events will be reportable to the Sponsor up to 30 days after the last IMP administration.

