10.3.2 Causality

The assessment of relationship of adverse events to the administration of IMP is a clinical decision based on all available information at the time of the completion of the case report form. The following categories will be used to define the causality of the adverse event:

Category	Definition
Definitely:	There is clear evidence to suggest a causal relationship, and other possible contributing factors can be ruled out.
Probably:	There is evidence to suggest a causal relationship, and the influence of other factors is unlikely
Possibly	There is some evidence to suggest a causal relationship (e.g. the event occurred within a reasonable time after administration of the trial medication). However, the influence of other factors may have contributed to the event (e.g. the patient's clinical condition, other concomitant events).
Unlikely	There is little evidence to suggest there is a causal relationship (e.g. the event did not occur within a reasonable time after administration of the trial medication). There is another reasonable explanation for the event (e.g. the patient's clinical condition, other concomitant treatments).
Not related	There is no evidence of any causal relationship.
Not Assessable	Unable to assess on information available.

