12.3.3 Secondary outcome analysis

Summary measures of the secondary endpoints will be presented (mean, standard deviation, median, interquartile range for continuous variables, percentages for categorical variables) by treatment group and for both baseline and end of trial follow-up visits. The percentage of missing data will be summarised.

- Time until resolution of first exacerbation will be compared between the active treatment and placebo groups, using a log-rank test. Cox regression analysis will also be conducted adjusting for important baseline covariates.
- The number of treatment-related adverse events will be analysed by using (over dispersed) Poisson regression or a suitable zero-inflated model and adjusted for treatment group and important baseline covariates.
- Exacerbation frequency: The rate of exacerbations experienced during the study period will be analysed by using (over dispersed) Poisson regression or a suitable zero-inflated model and adjusted for treatment group and important baseline covariates and with length of follow-up as an offset.
- Frequency of antibiotic courses: The rate of antibiotic courses received for patients in the active treatment and placebo groups will be compared using (over dispersed) Poisson regression or a suitable zero-inflated model adjusting for treatment group and important baseline covariates.
- The rate of hospital attendances during the study period will be analysed by using (over-dispersed) Poisson regression or a suitable zero-inflated model and adjusted for treatment group and important baseline covariates.
- Changes in respiratory healthcare status, assessed using SGRQ and CAT. SGRQ (score between 0 and 100) and CAT (score between 0 and 40) from baseline to day 90 will be modelled as a normally distributed random variable by using a suitable transformation (e.g. a Box-Cox like transformation to remove skewness and possible boundary effects). Any analysis will be adjusted for baseline scores, treatment, and other important baseline covariates. Repeated measures analysis will be used to assess treatment effects over time during the follow-up period.

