The percentage of missing data will be summarised and spurious data double checked as far as possible. Primary analysis will be intention to treat, and so every effort will be made to collect all follow-up data from non-compliers and patients who discontinue treatment. All patients will be analysed from the date of randomisation until end of follow-up period or the date of drop-out. The primary analysis will therefore assume patients who drop-out of the trial do so 'at random'.

Secondary outcome analysis

For each secondary outcome, two analyses will be undertaken – the first adjusting for centre and the baseline value of the endpoint being analysed (where available), and the second also taking into account the additional baseline characteristics specified in the supporting analysis of the primary outcome above.

When modelling continuous data, transformations will be undertaken as necessary to normalise the data. Where appropriate, analyses will take account of length of follow up as an offset, and also account for differences in at-risk periods. Summary measures of the secondary outcomes will be presented (mean, standard deviation, median, interquartile range for continuous variables, percentages for categorical variables) by treatment group and for both baseline and end of trial follow-up visits. The percentage of missing data will be summarised.

Secondary outcomes

- Time until *resolution* of first exacerbation will be compared between the active treatment and placebo groups, using Cox proportional hazards regression, stratified by centre.

• Duration of first exacerbation: dur

- The number of treatment-related adverse events will be analysed by using negative binomial regression. Negative binomial regression models collapse to Poisson regression if there is no overdispersion.

• Number of treatment-related AEs: trt.rltd.aes

- Exacerbation frequency: The rate of exacerbations experienced during the study period per person-year will be analysed by using negative binomial regression.

• Number of exacerbations: excns

- Frequency of antibiotic courses: The rate of antibiotic courses received for patients in the active treatment and placebo groups will be compared using negative binomial regression.

- The rate of hospital attendances during the study period will be analysed by negative binomial regression. .

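### The only adverse-event comparison planned by arm is of treatment-related events, so adverse events, serious adverse events and deaths judged unrelated are not compared between the randomised groups

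*SAP*

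**What the plan says.** The SAP, under Secondary outcomes, states: "The number of treatment-related adverse events will be analysed by using negative binomial regression". The one analysis variable it names for adverse events is "Number of treatment-related AEs: trt.rltd.aes". The by-arm summary tables have the same scope: "Summary measures of the secondary outcomes will be presented", and the secondary outcomes include no other adverse-event measure.

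The protocol agrees. Sections 4.2 and 12.1.2 list treatment-related adverse events as the outcome, and section 12.3.3 says: "The number of treatment-related adverse events will be analysed by using (over dispersed) Poisson regression or a suitable zero-inflated model". The in-trial review with the investigator and steering committee (protocol section 12.5; SAP, Interim analysis) is also worded in terms of treatment-related events.

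Collection is wider. Section 10.2: "All adverse events will be recorded in the paper CRF (which is the source data), whether believed to be related or unrelated to the treatment". Section 10.6 has all deaths notified to the sponsor whatever their cause. Relatedness is decided case by case under section 10.3.2: "The assessment of relationship of adverse events to the administration of IMP is a clinical decision based on all available information", on a six-category scale.

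**The concern.** In a double-blind, placebo-controlled trial, randomisation is what shows whether the drug causes an excess of events. A causality judgement made one patient at a time comes before that comparison and decides which events enter it. Events judged unrelated are excluded, and with them any drug effect that nobody recognised as one.

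Blinding makes mistaken judgements similar in the two arms, so the treatment-related comparison need not be biased towards either. It does not bring back the excluded events. A harm that clinicians do not connect with a one-week antibiotic course would be recorded in the CRF but would appear in no planned between-arm analysis of adverse events. The same holds for a death or serious event judged unrelated.

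**Working it through.** The main check sets the documents side by side. No figure in either bears on the point, so there is no stated result to reproduce.

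**What is recorded, and what is compared by arm**
- All adverse events: recorded (protocol 10.2). Compared by arm: only those judged treatment-related.
- Serious adverse events: recorded in the CRF and adverse-event log (protocol 10.2, 10.4). No by-arm comparison or table in either document.
- Deaths: all reported (protocol 10.6). No by-arm comparison or table.
- Hospital attendances, exacerbation rate, antibiotic courses and ciprofloxacin resistance: compared by arm with no causality filter (SAP, Secondary outcomes).

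The gap is therefore in adverse events, serious adverse events and deaths judged unrelated. One related omission is that neither document says which of the six causality categories count as treatment-related.

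**Does removing the filter detect harm better?** An illustration shows what the choice depends on. Everything here is assumed except the sample size: n = 138/2 = 69 per arm (SAP, Sample size), Poisson counts, a true excess d = 0.10 events per patient, background rate b per patient, a fraction s of drug-caused events judged related, and a fraction f = 0.10 of background events wrongly judged related.

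- All events: z = d / √[(b + b + d)/n]
- Related events: z = sd / √[(fb + fb + sd)/n]

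With b = 1.5:
- All: 0.10 / √[(1.5 + 1.6)/69] = 0.10/0.212 = 0.47
- Related, s = 0.6: 0.06 / √[(0.15 + 0.21)/69] = 0.06/0.0722 = 0.83
- Related, s = 0.2: 0.02 / √[(0.15 + 0.17)/69] = 0.02/0.0681 = 0.29

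With b = 0.5:
- All: 0.10 / √[(0.5 + 0.6)/69] = 0.10/0.1263 = 0.79
- Related, s = 0.6: 0.06 / √[(0.05 + 0.11)/69] = 0.06/0.0482 = 1.25
- Related, s = 0.2: 0.02 / √[(0.05 + 0.07)/69] = 0.02/0.0417 = 0.48

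For a small excess, the ratio of related to all-event z is about s/√f, so the filter helps when f < s². With f = 0.10 it helps when s exceeds about √0.10 = 0.32. A well-recognised reaction shows more clearly in the related count. A poorly recognised one shows more clearly in the all-event count, and at s = 0 the related count shows no excess at all. Neither comparison makes the other unnecessary.

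**The case against.** The strongest reply is that the SAP carries out the outcome that the protocol prespecified, for a licensed drug given for one week. All secondary outcomes are declared hypothesis-generating, an independent data monitoring committee assesses safety data (protocol 10.2), and further analysis follows if the drug behaves outside its known profile. This limits the consequence, and no prespecified efficacy conclusion depends on the adverse-event model. But committee review is monitoring, not a prespecified reported analysis, and none of these provisions supplies an all-cause comparison.

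Four stronger readings are tempting, and the documents do not support them.
- *That treatment-related events are the only safety comparison.* The unfiltered comparisons listed above contradict this, and some harms judged unrelated would be counted among hospital attendances.
- *That dyspnoea and fever will be attributed to COPD and lost.* Protocol section 3.4 lists both as possible drug risks and prompts thought about causality. Increased dyspnoea is a major diary symptom and fever a minor one in the primary outcome (section 12.1.1), so two consecutive days of both can count as an exacerbation, subject to the symptom-free-days rule. Treated worsening also counts. Isolated or mild episodes could still be missed, which is a much narrower point.
- *That the causality scale forces late events into the unlikely category.* The timing phrase, "the event did not occur within a reasonable time after administration of the trial medication", is given only as an example, the length of time is undefined, and the category goes on to mention another reasonable explanation.
- *That the treatment-related analysis should be demoted because it understates harm.* An understated excess is not the same as weaker detection. The illustration shows the filter gaining signal-to-noise when attribution is reasonably accurate.

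One further objection stands in full. Protocol section 10.4 expects uncomplicated COPD admissions to be frequent and treats them as a study end-point. Pooling them with other serious events would let a benefit on exacerbations offset harm elsewhere.

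**Conclusion.** The point holds for adverse events. Both documents restrict the by-arm analysis and summary to events judged treatment-related, although all events are recorded and all deaths reported. This is a stated filter resting on clinical judgement, not a missing detail. Adverse events, serious adverse events and deaths judged unrelated have no planned comparison as such between the randomised groups.

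No numerical size can be given. Any figure for hidden excess would rest on an assumed attribution accuracy and an assumed event rate, and the illustration's results depend on those choices. The change is worth making because it completes the account of harms at little cost, not because the treatment-related analysis is wrong.

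**What to change.** Keep the prespecified treatment-related model. Before unblinding, add to the SAP a by-arm comparison, regardless of causality, of:
- all adverse events;
- all serious adverse events;
- deaths.

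For each, report the number of patients with at least one event and the number of events, using the same negative binomial model for counts where numbers allow. Show COPD exacerbation events separately, so that an efficacy effect cannot mask other harms. Count serious events from the CRF, since section 10.4 exempts some of them from the sponsor's form. State which causality categories make up the treatment-related count.

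Timing matters. The SAP shows the arm variable as not yet released, so an addition now would be prespecified; after unblinding it would be post hoc. The cost is one more model and table, from data already collected. Background events will make the all-cause comparison noisier than the treatment-related one, so the two should be read together.

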- Lung function: Changes in FEV1, FEV1 as % predicted, and FEV1/FVC ratio and FVC at day 90 from day 0 will be modelled separately as continuous outcomes and assumed to be normally distributed (an appropriate transformation will be applied before analysis if required). Analyses will be adjusted for baseline values, treatment, and other important baseline covariates. Repeated measures analysis will be used to assess treatment effects over time during the follow-up period.
- Change in CRP from study entry to 90 days will be modelled as a normally distributed random variable by using a suitable transformation (e.g. a Box-Cox like transformation to remove skewness and possible boundary effects). Any analysis will be adjusted for baseline CRP, treatment, and other important baseline covariates. Repeated measures analysis will be used to assess treatment effects over time during the follow-up period.

- Resistance patterns (not resistant, resistant) will be analysed using logistic regression and adjusting for treatment group, baseline values and other important baseline covariates.
- The change in bacterial load from trial beginning to end will be analysed using multiple tobit regression and adjusting for baseline values and other relevant baseline covariates. Values below limits of detection will be treated as left censored observations in the tobit regression analysis.
- Adherence as assessed by pill counts. The number of pills taken over total number dispensed will be modelled using logistic regression (Binomial distribution with logit link). The difference in percent adherence will be assessed between treatment groups.
- Cost-effectiveness will be assessed as part of a future study (WP5)

This study is not powered to test these secondary outcomes – only the primary outcome. As such, analyses of the secondary outcomes will be hypothesis generating only.

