
- Post-bronchodilator spirometry: Specifically the measurement of volume and flow of air inhaled and exhaled. The parameters measured will be the Forced vital

capacity (FVC) and Forced expiratory volume (FEV) at 1 second. The FEV1/FVC ratio and FEV1 as a percentage of predicted normal value will be computed to assess FEV1 and FVC. A minimum of three spirometry readings will be taken to assess FEV1 and FVC. The highest individual FEV1 and FVC readings will be used to calculate the FEV1/FVC ratio and for comparison with the predicted normal value. This will be taken at screening visit (V1), first follow up (V2), second follow up (V3), end of study (V4) and if patient presents with exacerbation during study (EX).

The spirometry will be considered post-bronchodilator if the patient has taken their usual long-acting bronchodilator medication OR if they have had a shortacting bronchodilator administered in clinic 10-15 minutes prior to spirometry testing.

- Diary Cards: These cards will be used to measure changes in symptoms/side effects, as well as in defining exacerbations for the primary endpoint, and therefore will be carefully explained to the patient at this time, and at every visit (as spirometry).
- General baseline characteristics: Age, gender, smoking status, self-reported exacerbation frequency in the previous year, Smoking history (pack years)
- Basic physiological measurements and clinical examination: These include blood pressure, oxygen saturations, pulse oximetry, respiratory rate, pulse rate, height, weight, BMI and a full clinical exam. These will all be performed in the usual manner, and measured at V1 and at exacerbation visit (EX).
- Pill count: This will be taken at V2.
- CRP Blood samples: Will be collected and analysed for CRP levels to measure presence of inflammation in the body. This is measured in milligrams per litre of blood (mg/L), and will be measured at every visit (as spirometry).
- Serum samples: will be taken at every visit (as spirometry) and stored at -80C for future analysis of inflammatory markers.
- Sputum samples: If spontaneously expectorated, the sputum samples will be collected and analysed to measure bacterial load in the lung. Concentrations will be log transformed and expressed as log10 CFU (colony forming units)/ml. Collection of sputum is not a requirement for study entry and this will therefore form a subgroup analysis. The sputum samples will be collected from patients at

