- Changes in respiratory healthcare status, assessed using SGRQ. SGRQ (score between 0 and 100from baseline to day 90 will be modelled as a normally distributed random variable. Linear regression will be used,

- Changes in respiratory healthcare status, assessed using CAT. CAT (score between 0 and 40) from baseline to day 90 will be modelled as a normally distributed random variable. Repeated measures analysis will be used to assess treatment effects over time during the follow-up period.

- Lung function: Changes in FEV1, FEV1 as % predicted, and FEV1/FVC ratio and FVC at day 90 from day 0 will be modelled separately as continuous outcomes and assumed to be normally distributed. Repeated measures analysis will be used to assess treatment effects over time during the follow-up period.

- Change in CRP from study entry to 90 days will be modelled as a normally distributed random variable. Repeated measures analysis will be used to assess treatment effects over time during the follow-up period.

- Resistance patterns (not resistant, resistant) will be analysed using logistic regression.

- The change in (log10) bacterial load from trial beginning to end will be analysed using parametric survival regression(linear regression with censored outcome data). Values below limits of detection will be treated as left censored.

- Adherence as assessed by pill counts. The number of pills taken over total number dispensed will be modelled using logistic. The difference in percent adherence will be assessed between treatment groups.

- Cost-effectiveness will be assessed as part of a future study (WP5)

This study is not powered to test these secondary outcomes – only the primary outcome. As such, analyses of the secondary outcomes will be hypothesis generating only.

Subgroup analyses

Relevant subgroups may be analysed (including patients who gave sputum samples), allowing the incorporation of any important new information and methodological concerns identified between now and the time of writing the analysis plan. However, such analyses should be undertaken before unblinding, and keeping in mind that any analyses will be hypothesis generating only.

Sensitivity analysis

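### The left-censoring rule for change in bacterial load is not limited to day-90 values, and it points the wrong way when the baseline is undetectable

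*SAP*

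**What the plan says.** The SAP, under Secondary outcomes, takes the change in log10 bacterial load from start to end of trial as the outcome. It says this "will be analysed using parametric survival regression(linear regression with censored outcome data"), and continues: "Values below limits of detection will be treated as left censored".

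Protocol 12.3.3 is parallel: "The change in bacterial load from trial beginning to end will be analysed using multiple tobit regression", with adjustment for baseline values, and "Values below limits of detection will be treated as left censored observations in the tobit regression analysis".

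Two other statements bear on the point. For every secondary outcome the SAP (Secondary outcome analysis) plans two models, "the first adjusting for centre and the baseline value of the endpoint being analysed (where available"), and the second adding further covariates. Under Study variables and endpoints, the SAP gives the scale as log10 CFU/ml and notes that "Collection of sputum is not a requirement for study entry", so the outcome exists only for an unstated subset of those randomised.

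Neither document says what happens when the baseline value, or both values of a pair, lie below the detection limit.

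**The concern.** A change is the difference of two measurements, and either may be below detection. A left-censoring rule suits a day-90 value below the limit. Applied to a baseline value below the limit, it reverses the inequality and sets aside a day-90 value that was measured.

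Undetectable baselines are plausible here. Day-0 sputum is taken 14 ± 3 days after the start of treatment for the index exacerbation, which includes 5–14 days of a non-quinolone antibiotic (Protocol 6.1 and 8.4). Patients may also enter on CRP alone. Bacterial load bears directly on what an antibiotic does, and sputum pairs will be few, so information should not be lost to an unclear coding rule.

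**Working it through.** **Direction of censoring.** Let L be the detection limit, Y0 and Y90 the log10 loads, and D = Y90 − Y0.

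- Only Y90 undetectable: Y90 < L, so D < L − Y0. Left-censored; the rule is right.
- Only Y0 undetectable: Y0 < L, so D > Y90 − L. Right-censored; the rule reverses it.
- Both undetectable: D has no bound. Left-censoring invents one.

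The limit for D is patient-specific, L − Y0, and does not exist when Y0 is undetectable.

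**What baseline adjustment does.** If D = a + b·arm + c·Y0 + e, then Y90 = a + b·arm + (1 + c)·Y0 + e. The treatment coefficient b is the same, and Y90 < L is the same event as D < L − Y0. With Y0 observed, modelling change with day-90 left-censoring is therefore the same as day-90 tobit regression. With Y0 undetectable, only the day-90 form stays defined, and the missing detail becomes the covariate value.

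**Size.** The documents give no detection limit, undetectable share, SD, target effect, power or number of pairs for this outcome, so there is no plan figure to reproduce. All inputs below are assumed: bivariate normal log10 load, true effect −1.0 log10, 5% two-sided tests, maximum-likelihood censored regression. The literal rule left-censors any pair with an undetectable value. The comparator is day-90 tobit. Both include baseline as covariate.

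| Setting | Baseline undetectable | Literal: estimate, power | Day-90 tobit: estimate, power | Loss (points) |
|---|---|---|---|---|
| n=60, SD 1.3, corr 0.5 | 10% | −0.98, 88.5% | −1.00, 91.5% | 3.0 |
| same | 30% | −0.96, 74.9% | −0.99, 86.0% | 11.1 |
| same | 50% | −0.98 (median −0.89), 51.2% | −1.00, 76.3% | 25.1 |
| n=100, SD 1.3, corr 0.5 | 10% | −0.98, 98.5% | −0.99, 98.8% | 0.3 |
| same | 30% | −0.94, 91.4% | −0.98, 97.0% | 5.6 |
| same | 50% | −0.92, 74.6% | −0.98, 94.0% | 19.4 |
| n=60, SD 1.3, corr 0.8 | 30% | −0.94, 97.1% | −0.97, 98.6% | 1.5 |
| same | 50% | −0.92, 84.3% | −0.97, 93.9% | 9.6 |
| n=60, corr 0.5, common drift +1 log10 | 50% | −0.92, 60.9% | −0.99, 87.5% | 26.6 |
| n=70, SD 1.5, corr 0.6 (medians) | 10% | −0.90, 88% | −0.95, 92% | 4 |
| same | 30% | −0.94, 78% | −0.97, 86% | 8 |
| same | 50% | −0.86, 51% | −0.98, 77% | 26 |

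Estimates are means except where marked. The SD 1.3 rows use at least 800 replicates, so at 75% power the Monte Carlo standard error is √(0.75 × 0.25/800) = 1.5 points. The n=70 rows use 150, so at 51% it is √(0.51 × 0.49/150) = 4.1 points.

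Across all settings run without a time trend (correlation 0.2 to 0.8), the loss was about 0–3 points at 10%, 1.5–14 at 30% and 10–25 at 50%. The n=70 run extends the first range to 4, and the drift case the last to 27.

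Shrinkage under the literal rule is 1.0 − 0.98 = 2% to 1.0 − 0.92 = 8% on means, and up to 1.0 − 0.86 = 14% on medians.

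The comparator in the SD 1.3 rows omits the undetectable-baseline indicator. Where it was added, power moved by less than 2 points and estimates were −0.98 to −1.00.

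**Type I error** (n=60, corr 0.5, 30% undetectable, 800 replicates): literal rule 5.9%; day-90 tobit 6.5%, or 6.8% with the indicator; ANCOVA on fully observed data 6.2%. The Monte Carlo standard error at 5% is √(0.05 × 0.95/800) = 0.8 points. Neither approach shows material inflation.

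**The case against.** A reader might infer that the SAP codes every below-detection value, baseline included, as left-censored, and so will shrink the effect and lose substantial power. The documents do not support that strength. The SAP speaks of censored outcome data, which ties censoring to the outcome, and both documents adjust for baseline. Read together, these allow exactly the sound analysis: left-censor day-90 values and carry baseline as a covariate. Most of the remedy is then already in the plan.

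The consequences are also conditional. With the planned covariate the shrinkage is modest. Without it, mean estimates ranged from −0.85 to −1.07, so bias is not always towards zero. At 10% undetectable the power loss is negligible, and at 30% with correlation 0.8 it is 1.5 points. Nothing in the documents supports or excludes the high shares at which the loss is large. Both documents call secondary analyses unpowered and hypothesis generating.

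All of this stands, and it limits the point. It does not remove it. The sound reading is permitted but not written down, the outcome is still specified as a change, and an analyst applying the sentence to any undetectable value would be following the text. The phrase in the SAP about a baseline being available does not say whether an undetectable baseline counts as available.

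**Conclusion.** The rule is ambiguous, and its literal application to baseline values is wrong in direction. That part is algebra and needs no assumptions. The cost depends on the share of undetectable baselines, which is not given: on the assumed inputs above, little at about 10% and material for power by 50%, with modest shrinkage and no material type I inflation. The documents do not show that the faulty reading is the intended one. Severity is low, because the outcome is a hypothesis-generating secondary one measured only in patients who expectorate spontaneously.

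**What to change.** State in the SAP that the outcome is day-90 log10 bacterial load, not the change, analysed by tobit regression and left-censored at the detection limit. The covariates are arm, centre, baseline log10 load (set to the limit if undetectable) and an indicator for an undetectable baseline. Pairs with both values undetectable then enter as left-censored day-90 values, with a defined likelihood contribution. The detection limit should be stated too.

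Simply recoding baseline-undetectable pairs as right-censored changes is not a good substitute. In the same simulations it overstated the effect (−1.02 to −1.16 with the covariate, up to −1.58 without, for a true −1.0).

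The cost is one or two sentences, with the same data and the same class of model. It should be settled before the treatment codes are released.
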